# 8.10 Pharmacodynamic Biomarkers

The trial will include pharmacodynamic assessments based on changes in selected cytokines and other activation markers. Cytokine samples will be taken at the same time points as for PK sampling – see Table 1-3 and Table 1-4.

Furthermore, cytokine samples will be taken at disease progression or treatment discontinuation. If an adverse event of CRS is suspected, cytokines should be obtained at an unscheduled visit to support the diagnosis.

Table 1-7 (Part 1A) and Table 1-8 (Part 1B) provide details of biomarker assessments to be performed during dose escalation. Samples will be collected from all patients. Biomarker assessments will include tumor biopsy, blood sampling for cytokine analysis, and further analysis, that may include immune phenotyping, tumor mutational burden and TCR profiling. Further details regarding sample types, volumes etc. are provided in the laboratory manual.

Samples may be analyzed to monitor pharmacodynamics by evaluating changes in systemic and intratumoral immune response (e.g. immunophenotyping of immune cells in peripheral blood, absolute and relative changes compared to baseline in tissues and/or peripheral blood mononuclear cells [PBMCs]) in blood and tumor tissue compared to baseline. Additionally, targeted sequencing may be performed for profiling of T-cell receptors (TCR profiling) in order to identify potential markers that may predict clinical response (see Section 8.11).

Samples for biomarker analysis can be used up to 5 years after the end of the trial. Biomarker analyses may be deferred or not performed, if during or at the end of the trial, it becomes clear that the analysis will not have sufficient scientific value for biomarker evaluation, or if there is

not enough sample to allow adequate evaluation. In the event that the trial is terminated early or shows poor clinical efficacy, completion of biomarker assessments is based on justification and intended utility of the data.

#### 8.11 Genetics

Where required by local or country specific regulations, each patient must sign a separate informed consent form if he or she agrees to genetic testing (DNA and RNA) of the collected samples.

These analyses may include the following:

- i. Identification of tumor specific mutations on a DNA level to evaluate tumor mutational burden (TMB) as a potential predictive marker
- ii. Identification of mRNA expression pattern of immune-relevant genes in the tumor as a potential predictive marker
- iii. Profiling of T-cell receptors (TCRs) in the periphery and tumor as a potential predictive marker as well as a surrogate for pharmacodynamics

If a patient refuses to consent to DNA and RNA research in these specific regions, the patient is still eligible to participate in the trial.

## 8.12 Immunogenicity Assessments

Immunogenicity is not being evaluated in this trial.

#### 9 Statistics

## 9.1 Statistical Hypotheses

No statistical hypotheses are planned to be tested in this trial.

## 9.2 Sample Size Determination

The sample size for Parts 1A and 1B is driven by the 3+3 trial design and will range from three to six DLT evaluable patients per cohort depending on the number of DLTs which may occur. In total, between 6 to 60 DLT evaluable patients are planned to be enrolled in the Part 1A, and between 6 to 30 DLT evaluable patients are planned to be enrolled in the Part 1B.

## 9.3 Analysis Sets

#### **Modified Intent to Treat Set**

The modified ITT (mITT) set is defined as all patients who are assigned to BNT411 and have a baseline and at least one on-treatment/post-treatment tumor response assessment.

## **Safety Set**

The safety set is defined as all patients who received BNT411 (i.e. at least one dose of BNT411).

#### **DLT Evaluation Set**

The DLT evaluation set includes all patients from the safety set who either have completed the DLT evaluation period and meet the minimum exposure criterion or have experienced a DLT during the DLT evaluation period (Cycle 1).

Patients who do not experience any DLT during the DLT evaluation period are considered to be evaluable if they have been observed for minimum 21 days following the first dose and are considered to have sufficient safety data to conclude that a DLT did not occur. A patient is considered to have met the minimum exposure criterion if the relative dose intensity (RDI) of BNT411 in Cycle 1 is 100%.

Patients who are excluded from the DLT evaluation set will be replaced.

The DLT evaluation set will be used for the evaluation of DLTs in order to assess the MTD and the RP2D. The safety set will be used for all other safety analyses, while the mITT set will be used for efficacy analyses (Part 2 only).

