7 ANALYSIS SETS AND SUBGROUPS

7.1 Analysis sets

Enrolled Set

Enrolled set will have the patients with a valid date of informed consent.

Safety Set

The Safety set is defined as all patients who received BNT411 (i.e., at least one dose of BNT411).

DLT Evaluation Set

The DLT evaluation set includes all patients from the Safety set who either have completed the DLT evaluation period (i.e., have been observed for minimum 21 days following the first dose) and meet the minimum exposure criterion (i.e., when the relative dose intensity [RDI] of BNT411 in Cycle 1 is 100%) or have experienced a DLT during the DLT evaluation period (Cycle 1).

Patients who do not experience any DLT during the DLT evaluation period are considered to be evaluable if they have been observed for minimum 21 days following the first dose and are considered to have sufficient safety data to conclude that a DLT did not occur.

Patients who are excluded from the DLT evaluation set will be replaced.

Pharmacokinetic (PK) Full Set

The PK Full set will consist of all patients who receive at least one dose of BNT411 and have at least one quantifiable post-dose PK sample.

Pharmacokinetic (PK) Evaluable Set

The PK Evaluable set will consist of all patients in the PK Full Set with a sufficient number of quantifiable PK samples to reliably estimate one or more PK parameters.

Pharmacodynamic (PD) Set

The PD set is defined as all patients who received IMP (i.e., at least one dose of BNT411) and have at least one valid post-dose PD assessment.

The DLT evaluation set will be used for the evaluation of DLTs in order to assess the MTD and the RP2D. The Safety set will be used for all other safety analyses. The PK Full Set, PK Evaluable Set and PD analysis set will be used for the PK and PD summaries, respectively.

Most patient data listings will be based on the Safety set. The Enrolled set will be used to summarize the patient disposition summary and some patient data listings.

For the screened patients, the summary is not by cohort, the number and percentage of patients having failed screening (reported as screen failure in the electronic Case Report Form [eCRF]) will be presented along with a summary of the primary reason for screening failure.

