8.2 Patient disposition

Unless otherwise specified, all of the summaries will be presented by cohort and total within each trial part (Part 1A and Part 1B).

For the screened patients, the number and percentage of patients having failed screening will be presented along with a summary of the primary reason for screening failure. A summary of reason for violation of inclusion/exclusion criteria will also be presented. This summary is not by cohort.

The number and percentage of patients enrolled by site will be presented. The number and percentage of enrolled and treated patients will be presented by country and site including the number and percentage of IPDs (by cohort and total within each trial part).

The number and percentage of patients in each analysis set will be summarized by cohort and total within each trial part.

For each analysis set (e.g., Safety set, DLT evaluation set, PK Full set, PK Evaluable set and PD set) the number and percentage of patients being excluded from the analysis set will be presented by cohort and total along with a summary of the reasons for exclusion based on the Enrolled set.

For the Safety set the number and percentage of patients who are still on-treatment and percentage of treated patients who are off treatment will be summarized. Patients who are “off treatment” will be the patients who are discontinued from treatment. Also, for the Safety set the number and percentage of patients discontinued from each trial treatment (BNT411, atezolizumab, carboplatin, etoposide) will be presented along with a summary of the primary reason for treatment discontinuation as reported in the eCRF. All summaries will be by cohort within each trial part.

The number of patients that entered/not entered safety follow-up 1 and safety follow-up 2 (defined as had at least one data point collected in safety follow-up 1, safety follow-up 2, respectively) and the number of patients that had early discontinuation from the trial together with the primary reason for discontinuation will be summarized for the patients in the Safety set by cohort and total within each trial part.

In addition, total number of deaths will be summarized by cohort and total within each trial part for the Safety set.

A listing of patient disposition (including discontinuation from each trial treatment (BNT411, atezolizumab, carboplatin, etoposide) and discontinuation from trial) will be presented.

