8.5.1 Extent of exposure

The following dose exposure variables will be derived and summarized for each treatment (BNT411 in Part 1A also BNT411, atezolizumab, carboplatin, and etoposide in Part 1B). The summaries will be based on patients in the Safety set and will be repeated for DLT evaluation set. The summary for the DLT evaluation set will be restricted to the exposure data from the first cycle (21 days).

- Number of treated cycles.
- Number of BNT411 infusions.

- Number of atezolizumab, carboplatin and etoposide infusions (Part 1B).
- (Actual)Treatment Duration (weeks) defined as follows: (Date of last administration - Date of first administration + Planned Duration) / 7, where the Planned Duration (days) is defined as the planned time between two consecutive administrations. In Part 1A, planned duration for BNT411 is one week for the first four cycles, followed by once every 3 weeks. In Part 1B, planned duration for BNT411 for the first four cycles is 6 days if the patients' last dose was the first dose within any cycle, 7 days if the patients' last dose was the second dose within any cycle and 8 days if the patients' last dose was the third dose in within any cycle. After 4 cycles planned duration for BNT411 is 3 weeks. Planned duration for atezolizumab is every 3 weeks, for carboplatin it is 21 days apart till Cycle 4 and for etoposide planned duration is one day till day 3 of the Cycle 4. Actual treatment duration is calculated for each treatment separately.
- Planned Treatment Duration (weeks) defined as (scheduled date of last administration - scheduled date of first administration + Planned Duration) / 7. The scheduled date of last administration is the date at which the last administration should be given according to the CTP schedule. Planned duration is as above.
- (Actual) Cumulative Dose defined as sum of all administered doses for each trial treatment. BNT411 (μg) for Part 1A and Part 1B and atezolizumab (mg), carboplatin (mg), and etoposide (mg) for Part 1B. Calculated for each treatment separately.
- Planned Cumulative Dose defined as sum of all planned doses, separately, for each trial treatment. BNT411 (μg) for Part 1A and Part 1B and atezolizumab (mg), carboplatin (mg), and etoposide (mg) for Part 1B.
- Dose Intensity is defined as Cumulative Dose for that trial treatment (unit for that trial treatment) / (Actual) Treatment Duration (weeks) for that trial treatment.
- RDI % (using units for BNT411) is defined as follows:

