$$\text{RDI (\%)} = \frac{\text{Actual Dose Intensity } \left(\frac{\mu\text{g}}{\text{week}} \right)}{\text{Planned Dose Intensity } \left(\frac{\mu\text{g}}{\text{week}} \right)} \times 100 = \text{DI} \times \text{TI} \times 100,$$

Where

$$\text{Actual Dose Intensity } \left(\frac{\mu\text{g}}{\text{week}} \right) = \frac{\text{(Actual) Cumulative Dose } (\mu\text{g})}{\text{(Actual) Treatment Duration (weeks)}}$$

$$\text{Planned Dose Intensity } \left(\frac{\mu\text{g}}{\text{week}} \right) = \frac{\text{Planned Cumulative Dose } (\mu\text{g})}{\text{Planned Treatment Duration (weeks)}}$$

$$\text{Dose Index (DI)} = \frac{\text{Total Administered Dose } (\mu\text{g})}{\text{Total Planned Dose } (\mu\text{g})}$$

$$\text{Time Index (TI)} = \frac{\text{Planned Treatment Duration (weeks)}}{\text{Actual Treatment Duration (weeks)}}$$

The units in the derivations above are for BNT411. For atezolizumab, carboplatin and etoposide the unit is mg.

The following variables will be presented with summary statistics for each trial treatment by cohort for each trial part:

- Number of cycles received (categorical, Cycle 1-2, 3-4, 5-6, 7-8, 9-10, 11-12, 13-14, 15-16, 17-20 21-24 and so on, aligned to the tumor assessments every 6 weeks and 12 weeks respectively)
- Number of BNT411 infusions (descriptive statistics)
- Number of BNT411 infusions (categorical, 1, 2, 3 and so on)
- Number of atezolizumab, carboplatin and etoposide infusions (descriptive statistics) (Part 1B)
- Number of atezolizumab, carboplatin and etoposide infusions (categorical, 1, 2, 3 and so on) (Part 1B)
- Treatment duration
- Cumulative dose
- Dose intensity
- RDI

Additionally, the RDI will be presented categorically (i.e., number and percentage of patients with RDI of <60%, 60-<80%, ≥80%). Moreover, the number and percentage of patients with any dose delay, 4-7 days, > 7 days of dose delay and with any dose modification, dose reduction, dose increase, at least one dose modification and at least two dose modification and any dose interruption will be presented separately for each trial treatment for each trial part. Dose reduction and dose increase will be calculated as planned dose - given dose or total dose.

All the above mentioned dose exposure variables will be presented in a by-patient listing. A by-patient listing of treatment administration will be presented.

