The number and percentage of patients reporting DLTs will be summarized by PT nested within SOC for each cohort by trial part using the DLT evaluation set.

A separate listing of DLTs will be presented, including reported term, SOC, PT, time of onset, duration, outcome, relationship to trial treatment, NCI CTCAE grade, and seriousness including dose exposure data during the first cycle (i.e., 21 days).

Overall summary of adverse events (AE)

The number and percentage of patients reporting at least one AE will be summarized for each of the following AE types by cohort and trial part (Parts 1A and 1B). Related applies to a separate summary for BNT411 in Part 1A and BNT411, atezolizumab, carboplatin, and etoposide and any NIMP/IMP in Part 1B, unless otherwise specified :

- any TEAE
- related TEAE
- grade ≥ 3 TEAE
- related grade ≥ 3 TEAE

- any treatment-emergent serious AE (TESAE)
- related TESAE
- TESAE leading to death
- Related TESAE leading to death
- TEAEs leading to dose reduction and dose interruption (BNT411 in Part 1A or BNT411, atezolizumab, carboplatin, and etoposide in Part 1B)
- TEAE leading to permanent discontinuation of treatment (BNT411 in Part 1A or BNT411, atezolizumab, carboplatin, and etoposide in Part 1B)
- DLTs

Analyses of adverse events

The number and percentage of patients reporting at least one TEAE will be summarized by PT nested within SOC for each of the above AE categories. If an SOC / PT is reported more than once for a patient, the patient will only be counted once for this SOC / PT. Strongest relationship or worst grade will be counted if a TEAE is reported more than once by the same patient for a SOC / PT. The common TEAE occurring in $\geq 10\%$ of the patients will be summarized separately.

All AE summary tables will be sorted in descending frequency order by SOC and PT within SOC.

Analyses of other adverse events (excluding serious AEs)

The number and percentage of patients reporting other TEAEs (excluding TESAEs) will be summarized by PT nested within SOC. If a SOC / PT is reported more than once for a patient, the patient will only be counted once for this SOC / PT.

All AE summary tables will be sorted in descending frequency order by SOC and PT within SOC.

TEAE by relationship

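### The Cycle 1 RDI-of-100% test for the DLT Evaluation Set does not implement the three-infusion rule: it passes Part 1A patients given one or two doses and fails fully dosed patients whose last dose fell on Day 16

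*Protocol*

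**What the plan says.** Protocol 4.1.1.1 and the Synopsis express eligibility for DLT assessment as a count: all three BNT411 infusions in Cycle 1. Protocol 4.1.1.1 replaces DLT-free patients who do not meet it.

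The analysis-set definition uses a rate instead. Protocol 9.3: "A patient is considered to have met the minimum exposure criterion if the relative dose intensity (RDI) of BNT411 in Cycle 1 is 100" percent. SAP 7.1 requires DLT-free patients to complete the observation period and also to "meet the minimum exposure criterion (i.e., when the relative dose intensity [RDI] of BNT411 in Cycle 1 is 100" percent. Neither section gives a tolerance, a rounding rule or a dose count. DLT-free patients must also have at least 21 days of observation and sufficient safety data. Patients with a DLT enter whatever their exposure, and excluded patients are replaced.

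The protocol does not define RDI. The only formula is in SAP 8.5.1. Actual duration in weeks is built from "Date of last administration - Date of first administration + Planned Duration) / 7", so its end point is the last dose received. For planned duration, "The scheduled date of last administration is the date at which the last administration should be given according to the CTP schedule". RDI is actual over planned dose intensity, which the SAP also writes as Dose Index times Time Index. The same section applies these variables to the DLT set: "The summary for the DLT evaluation set will be restricted to the exposure data from the first cycle (21 days").

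Under SAP 8.5.2 the number and percentage of patients with DLTs "will be summarized by PT nested within SOC for each cohort by trial part using the DLT evaluation set". Both documents name this set for assessing the MTD and RP2D.

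**The concern.** A rate is standing in for a count. Because the denominator runs only to the last dose received, missing the final dose or doses shortens it along with the numerator, and a late final dose lengthens it. An under-dosed patient can therefore look fully exposed, and a fully dosed patient can look under-exposed.

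Both errors affect only DLT-free patients, so they change the denominator of the DLT proportion and never the numerator. Excluding compliant DLT-free patients raises the reported proportion; keeping under-dosed ones lowers it. Cohorts are planned at three to six evaluable patients, so one misclassification is visible. Dose levels 1 to 3 start as single-patient cohorts. There, one Day 16 exclusion would leave an unexpanded cohort with no evaluable patient until a replacement is treated.

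**Working it through.** **Inputs**

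- Cycle 1 dosing days: 1, 8, 15 in Part 1A and 2, 8, 15 in Part 1B (Protocol 6.1.1).
- Visit window for Day 8 and Day 15: ±1 day in both parts (Protocol Tables 1-1 and 1-2).
- Planned interval after the last dose: 7 days in Part 1A; 6, 7 or 8 days after the first, second or third dose in Part 1B (SAP 8.5.1).
- Assumption: every infusion given is a full planned dose, and RDI is not rounded.

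**Formula**

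Planned Cycle 1 duration is (15 − 1 + 7)/7 = 3 weeks in Part 1A and (15 − 2 + 8)/7 = 3 weeks in Part 1B. The plan is therefore 3 doses in 3 weeks, or 1 dose per week. With n doses received,

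RDI = 100 × n × 7 / (last day − first day + planned interval).

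**The plan's own figure.** Part 1A on Days 1, 8, 15: 3 × 7/(14 + 7) = 21/21 = 100%. Part 1B on Days 2, 8, 15: 3 × 7/(13 + 8) = 21/21 = 100%. On-schedule dosing reproduces the criterion.

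**Three full doses, either part.** Only the date of the last dose matters.

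| Last dose | RDI |
|---|---|
| Day 14 | 21/20 = 105% |
| Day 15 | 21/21 = 100% |
| Day 16 | 21/22 = 95.45% |

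The windows allow 3 × 3 = 9 date pairs (Days 7–9 by Days 14–16), three for each last-dose date. Six of nine miss exactly 100%. Three of nine still fail if the rule is read as at least 100%.

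**Part 1A, doses missed**

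| Doses received | RDI |
|---|---|
| Day 1 | 7/7 = 100% |
| Days 1, 7 | 14/13 = 107.7% |
| Days 1, 8 | 14/14 = 100% |
| Days 1, 9 | 14/15 = 93.3% |
| Days 1, 15 | 14/21 = 66.7% |

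As Dose Index times Time Index, Day 1 only is 1/3 × 3/1 and Days 1 and 8 is 2/3 × 3/2.

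**Other readings of the plan terms.** If planned dose and planned duration are both cut at the last dose received, the Part 1A results for Day 1, Days 1 and 8, and Days 1, 8 and 16 are unchanged: 100%, 100% and 95.45%. If planned dose stays at three while planned duration is cut, they become 33.3%, 66.7% and 95.45%. That mixed reading conflicts with the SAP's instruction to take the scheduled last administration from the protocol schedule. The Day 16 result is the same under all three.

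**Part 1B, final dose(s) missed.** The result depends on the reading.

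| Doses received | Full-cycle plan | Plan cut at last dose |
|---|---|---|
| Day 2 | 7/6 = 116.7% | 100% |
| Days 2, 7 | 14/12 = 116.7% | 13/12 = 108.3% |
| Days 2, 8 | 14/13 = 107.7% | 100% |
| Days 2, 9 | 14/14 = 100% | 13/14 = 92.9% |

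**Fixed 21-day denominator.** Three, two and one doses give 100%, 66.7% and 33.3%, the same as the Dose Index alone.

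**Effect on a reported proportion.** Take one DLT in six patients counted as evaluable under Protocol 4.1.1.1: 1/6 = 16.7%. If one DLT-free member had the third dose on Day 16 and was not replaced during the trial, the SAP set gives 1/5 = 20.0%. If instead a DLT-free Day-1-only patient was replaced under 4.1.1.1 but meets the SAP test and the other two conditions, it gives 1/7 = 14.3%.

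**The case against.** Neither set definition refers to SAP 8.5.1, and that section presents RDI as a summary variable. A programmer could take the first-cycle restriction as a 21-day denominator, which would give the intended result. But 7.1 uses the same term that 8.5.1 defines, and no fixed denominator is stated. If another formula was meant, it is unwritten and the set cannot be reproduced.

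The under-dosed patient may be stopped elsewhere, by the three-infusion rule in 4.1.1.1 or by a judgement that safety data are insufficient. That stands: scoring 100% meets the exposure criterion only. Neither provision helps the Day 16 patient, because SAP 7.1 joins completed observation and the exposure criterion with an and.

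A minimum is naturally met at 105% or 107.7%. This also has force: those scores fail only under strict equality. The nine date pairs are calendar combinations, not frequencies; the documents give no distribution of actual dosing dates.

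Finally, the mismatch could be seen. Reported outputs include "Number of BNT411 infusions (categorical, 1, 2, 3 and so on"), RDI minimum and maximum, and, for each set, "the number and percentage of patients being excluded from the analysis set will be presented by cohort and total" with reasons. The DLT listing carries Cycle 1 exposure. The RDI categories do not help, since their top band is 80% and above. These outputs could reveal an error but would not correct the set used for the primary summary.

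**Conclusion.** The concern holds. As written, the test and the three-infusion rule classify patients differently. The firmest part is the exclusion of a DLT-free, fully dosed patient whose third dose fell on Day 16: 95.5% in both parts under every reading tried, and not removed by reading the rule as a minimum. The 100% scores for one or two Part 1A doses follow from the formula as worded and fail only under the mixed reading; whether such patients enter the set also depends on the other two conditions. Part 1B results for missed final doses depend on the reading.

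The results assume full doses and no rounding. The size is one patient in a small denominator, illustrated by 14.3% to 20.0% around 16.7%. If the Protocol 9.3 test was applied during the trial, each Day 16 exclusion also cost a replacement patient. The documents do not show that the Safety Review Committee used this formula or that any escalation decision was affected. It should be corrected because the set supports a primary endpoint.

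**What to change.** Reconcile Protocol 4.1.1.1 and 9.3 with SAP 7.1 and 8.5.1. In SAP 7.1, derive the minimum-exposure flag from the protocol's existing three-infusion rule, using infusion count and the Dose Index against all three planned Cycle 1 doses, with a stated rounding tolerance. Alternatively, fix Cycle 1 duration at 21 days in both actual and planned intensity. State that doses within the visit window do not cause exclusion, and leave out-of-window doses to the existing observation and safety-data conditions. If a timing requirement was intended, the sponsor should write it explicitly. Keep RDI as a descriptive exposure variable.

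The cost is one SAP definition now and matching wording in Protocol 9.3 at the next amendment, which needs IRB/IEC approval (Protocol 10.1.1). One flag is re-derived from dosing data already collected; no new data are needed.
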